## 2 STUDY VARIABLES

### 2.1 Baseline Variables

#### 2.1.1 Demographics and Baseline Characteristics

- Age
- Gender
- Ethnicity
- Mobility
- Subject Social Profile
  - Living situation
  - Physical activity level
  - Lifestyle
  - Require assistance
- Height
- Weight

#### 2.1.2 History of leg ulcer

- Duration
- Wound location
- Latest ABPI value
- Recurrent ulcer
- Previous dressing
- Previous compression

#### 2.1.3 Medical and Surgical History

- Relevant medical history (general and with regard to venous disease/VLU)
- Relevant surgical history (general and with regard to venous disease/VLU)

#### 2.1.4 Wound Management

- Current wound management treatment

#### 2.1.5 Current Wound Status

- Estimated Wound Size
- Exudate amount (before debridement)

		Statistical Analysis Plan	
Protocol: Granulox01		Protocol No:	
Version: D1.0	Page 13 of 23		

- Predominant tissue (after debridement)
- Push Score Value
- Wound bed aspect (after debridement)
- Exudate nature

#### *2.1.6 Prior and Concomitant Medications*

[figure not shown]
### **2.2 Efficacy Variables**

#### *2.2.1 Primary Efficacy Variable –Confirmed Complete wound Closure (CCC)*

CCC is the primary variable and main efficacy criterion. It is defined as a blinded assessment and observation of 100% re-epithelialization, confirmed by a second visit 15 days later (+/- 3 days). If a wound graft is required, patients will be followed to observation of CCC.

Blinded quantification of each wound picture will be made using PictZar® Digital Planimetry Software.

CCC will be derived from two measurements of 100% re-epithelialization by PictZar®, 15 days (+/- 3 days) apart.

Statistical Analysis Plan

Protocol: Granulox01	Protocol No:
Version: D1.0	Page 14 of 23

#### **2.2.4 Acceptability and compliance**

During clinical visits, the patient-specific diary (completed by the study nurse) will provide input to the assessment of acceptability of care, ease of care, and compliance as follows:

- Assessment of acceptability of care by means of a 5-item scale (e.g. very poor, poor, average, good, very good). This will be performed at the final visit only.
- Assessment of ease of care by means of a 5-item scale (e.g. very poor, poor, average, good, very good). This will be performed at the final visit only.
- Evaluation of patient compliant to venous compression as either:
  - Fully compliance (defined as 7/7 days)
  - Moderately compromised compliance (defined as 1, 2 or 3 days/week maximum without compression)
  - No compliance (defined as >3 days/week without compression)

#### **2.2.5 Exploratory Efficacy Variables**

Measured at all schedule visits.

### **2.3 Safety Variables**

#### **2.3.1 Adverse Events**

Adverse Events (AE) and Serious Adverse Events (SAE) will be collected in the study to measure safety associated to study treatments from ICF signature until study completion. The definition of AE, Adverse Device Effect (ADE), SAE, Serious Adverse Device Effect

		Statistical Analysis Plan	
Protocol: Granulox01		Protocol No:	
		Version: D1.0	Page 16 of 23

(SADE), and Device Deficiencies (DD) and procedures for reporting SAE and SADE and DD that could have led to a SADE are presented in section 11 of the CIP.

### 3 STATISTICAL METHODOLOGY

#### 3.1 General Statistical Methodology

[figure not shown]
[figure not shown]
This study will use confirmative and explorative analyses. All analyses of primary and secondary variables will be performed on FAS. Subjects without any scheduled follow-up visit will not be included in any follow-up analyses. Complementary analysis of primary and secondary variables will also be performed based on PP population.

The primary analysis will be the comparison of Confirmed Complete wound Closure (CCC) between the two randomized groups using two-sided binary logistic regression analysis at significance level 0.05, on FAS with multiple imputation including the following covariates:

1. Country (as fixed effect)
2. Wound duration (<5 months;  $\geq$ 5 months)
3. Wound area after run-in period ( $<10 \text{ cm}^2$ ;  $\geq 10 \text{ cm}^2$ )

The essential analyses will be the comparison between the two randomised groups: the Granulox group and the Control group for primary and secondary variables. Analyses within each of the randomized groups will also be performed but without the same scientific value. For secondary efficacy variables the main analysis will be performed on change from baseline to final visit or at final visit, but analyses of change from baseline to the other visits will also be performed at week 1, 4, 8, 12 16 and 20. Final visit is defined as week 20 for subjects that have a 20 week visit, date of first CCC visit for subjects with CCC and for drop-outs with multiple imputation for week 20.

The study includes a fixed order of sequential testing of the following secondary variables.

The study utilized stratified randomization based on country, wound size, and wound duration. This is reflected by a stratified primary analysis adjusted for these variables. If baseline confounders are found, variables that differ between the two randomised groups and has a causal relation to the outcome variable, then complementary analyses will be performed adjusted for these variables.

For adjusted comparison between the two randomized groups, multivariable logistic regression will be used for dichotomous variables, analysis of covariance for continuous variables, Mantel-Haenszel pooling technique for ordered categorical variables and Cox proportional hazard model for time to event data.

The most important efficacy analyses both for unadjusted and adjusted analysis will be the calculation of the mean difference between the Granulox group and the Control group with 95% CI for continuous and dichotomous variables.

Continuous variable will be described with mean, SD, median, Q1, Q3, minimum and maximum and categorical variables with numbers and percentages. For dichotomous variables, for descriptive purpose, relative risk with 95% CI will also be calculated. Proc Genmod binary outcome variable and link = log. For time to event data Kaplan-Meier curves will be presented.

For analyses of change from baseline to other visits within each randomised group Fisher's non-parametric permutation test for paired observations will be used for continuous variables and Sign test for dichotomous and ordered categorical variables.

[figure not shown]
For continuous variables measured over time Box-plots will be given over visits by randomized group and Box-plots for change from baseline to each visit will be given by group. For selected secondary dichotomous and ordered outcome variables measured over time vertical bars will be given over visits by randomised group and vertical bars for change from baseline to each visit will be given by group.

All significance tests will be two-sided and conducted at the 5% significance level.

All analyses will be performed by using SAS® v9.4 (Cary, NC) or later.

### 3.2 Missing data.

		Statistical Analysis Plan	
Protocol: Granulox01		Protocol No:	
		Version: D1.0	Page 18 of 23

### **3.3 Patient Disposition and Data Sets Analysed**

The number of subjects included in each of the FAS, PP and safety populations will be summarized for each treatment group and overall. The number and percentage of subjects enrolled, randomized and treated will be presented. Subjects who completed the study and subjects who withdrew from study prematurely will also be presented with a breakdown of the reasons for withdrawal by treatment group for the FAS, PP and safety populations.

### **3.4 Protocol Violations/Deviations**

Major protocol deviations are those that are considered to have an effect on the primary analysis. A list of potential major protocol deviations will be generated programmatically from the data captured before the clean file meeting. The clinical monitors of the study will review the list and the finalisation of the major protocol deviations will be done at the clean file meeting.

The number and percentage of patients with major protocol deviations will be summarized per treatment group.

### **3.5 Demographics and Baseline Characteristics**

Demographics and baseline characteristics given in section 2.1 will be summarized by treatment group for the FAS and PP populations and analysed according to the methods described in section "General Statistical Methodology" above, 3.1.

### **3.6 Medical and Surgical History**

Listings of all medical and surgical history collected by the investigator will be produced.

### **3.7 Prior and Concomitant Medications**

Listings of all medications collected for each subject by the investigator will be produced.

### **3.8 Efficacy Analyses**

#### **3.8.1 Primary Efficacy Analysis**

The primary analysis will be the comparison of Confirmed Complete wound Closure (CCC) between the two randomized groups using two-sided binary logistic regression analysis at

significance level 0.05, on FAS with multiple imputation including the following stratified covariates:

- Country (as fixed effect)
- Wound duration (<5 months;  $\geq$ 5 months)
- Wound area after run-in period ( $<10$  cm $^2$ ;  $\geq$ 10 cm $^2$ )

Complementary analyses will also be performed for CCC between the two groups on the PP population.

Complementary analyses will also be performed for EOCR (CCC+PCC) between the two groups on the FAS population.

If baseline confounders are found, variables that differ clinically between the two randomised groups and has a causal relation to the primary outcome variable, then complementary analyses will be performed adjusted also for these variables with the same methods as for primary analysis.

Adjusted and unadjusted mean % differences between the two groups in CCC will also be given. The percentage of CCC in each group with 95% exact CI will be calculated. Unadjusted primary analyses of CCC by country and by country and centre will be presented with percentage and mean percent difference with 95% CI.

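### Extra covariates enter the complementary CCC analyses only when they look unbalanced between arms; a short list fixed in advance would serve better (minor)

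*SAP*

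**What the plan says.** The primary CCC analysis in SAP 3.8.1 is a logistic regression on the full analysis set, with country as a fixed effect, dichotomised wound duration and "Wound area after run-in period" as covariates. These are the stratification factors as the SAP gives them, and they are always in the model.

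The same section then provides for baseline confounders that may be found. They are defined as "variables that differ clinically between the two randomised groups" for which a second condition also holds, namely that the variable "has a causal relation to the primary outcome variable". If there are any, "then complementary analyses will be performed adjusted also for these variables with the same methods as for primary analysis".

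SAP 3.1 gives the rule for outcomes in general, with a slightly different trigger: "variables that differ between the two randomised groups and has a causal relation to the outcome variable". SAP 3.5 says that baseline characteristics are not only summarised by arm but also "analysed according to the methods described in section" 3.1, which sets significance tests at the two-sided 5% level.

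The visible text gives no size of difference that counts, no list of candidate variables, no criterion for a causal relation, and no statement of who decides or when. Protocol 5.2.2 and 5.2.2.1 do not contain the rule.

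**The concern.** In a properly randomised trial, a baseline difference between arms arises by chance. Making an observed difference a condition of entry therefore lets the particular randomisation decide which model is fitted. Two variables of equal prognostic value are treated differently only because one drifted apart between arms and the other did not.

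Covariate adjustment in a randomised trial gains precision by explaining outcome variation, and a balanced predictor does that as well as an unbalanced one. A rule driven by imbalance gives up part of that gain. It also produces a secondary CCC estimate whose covariates could not have been named beforehand, resting on judgements (clinically different, causal) that the visible text does not define. That makes the estimate harder to interpret beside the primary result, especially if the two disagree.

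**Working it through.** **Inputs.** N = 254 (SAP 1.2; SAP 1.4.1 allows an increase to at most 600). Two-sided 5% level (SAP 3.1). The allocation ratio is not printed, so 1:1 is assumed. The plan attaches no figure to the covariate rule, so there is none to reproduce. The derivation of 254 is redacted, and 254 is used here only as an input.

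**Step 1: how often a real predictor is left out.** Take one continuous predictor outside the strata and assume it meets the causal condition. With 127 per arm, the observed standardised difference has standard error √(1/127 + 1/127) = √(4/254) = 0.1255. For a threshold t, the chance of entry is 2 × (1 − Φ(t / 0.1255)).

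| Threshold for differing | t / SE | Enters | Left out |
|---|---|---|---|
| 0.10 | 0.80 | 0.43 | 0.57 |
| 0.15 | 1.20 | 0.23 | 0.77 |
| 0.20 | 1.59 | 0.11 | 0.89 |
| 0.246 (two-sided p<0.05) | 1.96 | 0.05 | 0.95 |

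If the sample rose to 600, the standard error would be √(4/600) = 0.0816. A fixed threshold of 0.1 would then leave a predictor out about 78% of the time (0.1 / 0.0816 = 1.22), and 0.2 about 99% (2.45). The p<0.05 row would not change.

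**Step 2: what that costs.** Simulated logistic trials, 2,500 per setting, N = 254. Randomisation was stratified on two binary factors with 50% prevalence each, and country was omitted. Five further independent standard-normal predictors were given an odds ratio of 1.5 per SD, and the treatment log-odds ratio was 0.75. All these effects are assumptions. Each row has its own simulated data, so compare within rows.

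| Threshold | Mean number selected of 5 | Power, strata only | Power, imbalance rule | Power, all five prespecified |
|---|---|---|---|---|
| 0.10 | 2.12 | 0.690 | 0.736 | 0.769 |
| 0.20 | 0.54 | 0.700 | 0.712 | 0.776 |
| p<0.05 | 0.27 | 0.683 | 0.690 | 0.757 |

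The share of the available power gain that the rule recovers is:
- at 0.1: (0.736 − 0.690) / (0.769 − 0.690) = 58%
- at 0.2: 0.012 / 0.076 = 16%
- at p<0.05: 0.007 / 0.074 = 9%

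**Step 3: type I error.** With no treatment effect, the imbalance rule rejected in 0.040, 0.044 and 0.050 of trials at the three thresholds. The prespecified model rejected in 0.049, 0.054 and 0.056. The Monte Carlo standard error is about √(0.05 × 0.95 / 2,500) = 0.004. The rule does not inflate the error rate.

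**Step 4: the estimate moves with the covariate set.** Mean treatment log-odds ratios were about 0.65 with strata only, 0.70, 0.67 and 0.65 under the rule, and about 0.78 with all five included. A conditional odds ratio depends on which covariates are in the model, so a covariate set chosen by chance also changes the quantity being estimated.

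**The case against.** The strongest reply has four parts.

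- **The important predictors are already in.** Protocol section 1 gives wound age and wound size as its examples of risk factors for non-healing, and both stay in every model in dichotomised form, together with country. This stands. A reader might infer that the rule leaves out nearly all real predictors, but the documents do not support that. The omission rates above apply only to predictors outside the strata, and whether strong ones exist is an assumption. Protocol 3.3.1 says no more than that the baseline data may affect healing.
- **The SAP does not say it selects by significance test.** This also stands. A reader might count 23 baseline items in SAP 2.1 and compute a chance of 1 − 0.95^23 = 69% that at least one differs at 5%. That figure imports a threshold that the SAP does not state and treats related items as independent. It also counts ulcer duration and wound size, which correspond to stratification factors (without them, 1 − 0.95^21 = 66%), and it ignores the causal condition. SAP 3.5 does not tie its baseline analyses to covariate selection.
- **The causal condition screens out irrelevant variables.** It is meant to, so the rule is not aimed at chance differences in variables of no prognostic value. It has no visible criterion, however, and it does nothing for a prognostic variable that happens to be balanced.
- **Checking whether a chance imbalance explains the result is a fair purpose.** It is. With an odds ratio of 1.5 per SD, an imbalance of 0.25 SD shifts the log-odds by about 0.25 × 0.405 = 0.10. A fixed list gives the same protection for every variable on it, without waiting for the imbalance to appear. Only variables off the list lose that check.

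**Conclusion.** The point holds and is minor. Observed imbalance is a necessary condition for an extra covariate in both sections. The complementary CCC model is therefore data-dependent, and it omits balanced predictors outside the strata between about 57% and 95% of the time over the thresholds tried. Those percentages rest on N = 254, 1:1 allocation and a continuous covariate. The power figures rest further on five independent predictors of assumed strength, and weaker or fewer predictors would make the loss smaller.

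Two stronger conclusions should not be drawn. First, a reader might infer that the primary result or its error rate is at risk. The primary model is fixed, the affected analyses are labelled complementary, and the simulations show no inflation even in those. Second, because the trial is open-label, a reader might infer that covariates will be chosen after outcomes are known. The visible text leaves the timing unstated. It places decisions on the analysis sets before database lock (SAP 1.5) and says nothing either way about covariates. Several SAP sections are blank in the public copy, so the timing may be settled there.

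**What to change.** - In SAP 3.1 and 3.8.1, delete the rule that adds covariates when they are found to differ between arms. This also removes the discrepancy between the two wordings.
- In SAP 3.8.1, name before unblinding one complementary CCC model. It should contain the primary covariates plus a short list that the sponsor chooses from the baseline variables in SAP 2.1 for expected prognostic strength, used whatever the observed balance and fitted by the same method as the primary analysis.
- In SAP 3.5, describe baseline characteristics by arm without significance tests.

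The cost is SAP wording only: no patients, visits or data items, and no conflict with the visible Protocol text on the primary analysis. The downside is that the sponsor gives up choosing covariates after seeing baseline balance. Any later adjustment for an unlisted variable would have to be reported as post hoc.

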### 3.8.2 Secondary Efficacy Analyses

### 3.8.3 Analyses of Exploratory Efficacy variables.

**3.8.4 Sub-group analyses****3.8.5 Exploratory Interaction analyses between treatment and baseline variables****3.9 Safety Analyses****3.9.1 Adverse Events**

All safety variables will be summarized and analysed descriptively by treatment group on the safety population.

The number of subjects reporting one or more AE/ADE/SAE/SADE/DD will be summarised by treatment group using frequency counts. If very few AE/ADE/SAE/SADE/DD these will only be listed.

The incidence (%) of AE/ADE/SAE/SADE/DD reported during the investigation will be summarised in an overview table and by treatment group.

**4 INTERIM ANALYSES****5 CHANGES OF ANALYSIS FROM PROTOCOL**

## **6 LISTING OF TABLES, FIGURES AND LISTINGS**

### **6.1 Listing of Tables**

Table Number	Table Title

Statistical Analysis Plan

Protocol:

**Granulox01**

Protocol No:

Version:

D1.0

Page 22 of 23

**6.2 Listing of Figures**

Statistical Analysis Plan

[figure not shown]
Granulox01

Protocol No:

Version:  
D1.0

Page 23 of 23

